10.4.4 Electrocardiogram

The ECG data will be obtained directly from the 12-lead ECG traces. These data include the QT interval calculated using the Bazett correction (QTcB), the QT interval calculated using the Fridericia correction (QTcF), the PR and QT intervals, the QRS duration, heart rate, and RR.

The ECG data will be summarized separately for Parts A and B by treatment, together with changes from baseline (see Section 10.1.1 for definitions of baseline). Figures of mean ECG data and mean change from baseline profiles will be presented separately for Parts A and B by treatment. The relationship between plasma concentrations of REMD-477 and changes from baseline in QTcF and QTcB will be explored graphically.

An outlier analysis will be performed including all individual post-dose QTcF and QTcB measurements (not the mean data), including all repeat and unscheduled readings. The frequency of subjects with a maximum increase from baseline in QTcB and QTcF intervals will be summarized for each treatment according to the following categories: >30 to 60 ms, >60, and \leq 30 ms. All incidences of >30 to \leq 60 ms, and >60 ms will be flagged on the listing. In addition, the frequency of subjects with QTcB and QTcF post-dose values will be summarized for each treatment, according to the following categories: >450 to 480, >480 to 500, >500, and \leq 450 ms. All incidences of >450 to 480, >480 to 500, and >500 ms will be flagged on the listing.

For Parts A and B separately the change from baseline of QT interval will be analyzed with a repeated measures ANCOVA. Dependent variables will be treatment, timepoint and the treatment by timepoint interaction. The change from baseline of the RR interval will serve as a covariate. Day is fitted as a repeated measure within subject. The estimated treatment means of the change from baseline of QT interval when change in RR interval equals zero will be presented for each timepoint. Also, the difference from placebo, the 95% CI of the difference from placebo, and p-value associated with the null-hypothesis of no difference will be presented for each timepoint.

An example of the SAS codes (abbreviated) is shown below:

```
proc mixed data=xxx;
  class subject day trtan;
```

```
model chg = chg_rr subject trtan day treatment*day;
repeated day / subject=subject type=csh;
lsmeans trtan*day / pdiff cl alpha=0.05;
estimate 'Est_CFB RR=0' intercept 1 chg_rr 0 trtan 1 0 avisit 1 0 0
trtan*avisit 1 0 0 0 0 0 /e;
...
run;
```

A similar analysis will be performed using the change from baseline in QTcF. Dependent variables will be treatment, timepoint, and the treatment by timepoint interaction. The baseline QTcF will serve as a covariate. Day is fitted as a repeated measure within subject. Treatment LS means will be presented for each timepoint. Also, the difference from placebo, the 95% CI of the difference from placebo, and p-value associated with the null-hypothesis of no difference from placebo, will be presented at each timepoint.

An example of the SAS codes is shown below:

```
proc mixed data=xxxx;
class subject day trtan;
model chg = base subject trtan day treatment*day;
repeated day / subject=subject type=csh;
lsmeans trtan*day / pdiff cl alpha=0.05; run;
```

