Heart rate and blood pressure will be analyzed with a repeated measures analysis of covariance. Dependent variables will be treatment, time and the treatment by time interaction. The baseline value will serve as a covariate. Subject will be used as a random effect. The least square mean of each treatment will be presented for each time. Also, the difference from placebo, the 95% confidence interval of the difference from placebo, and p-value associated with the null-hypothesis of no difference will be presented at each time.

Electrocardiogram

All on-study ECG data will be listed and may be plotted. The Bazett's (QTcB) and Fridericia's (QTcF) QT corrections will be computed.

Subjects will be categorized into the following groups per their maximum change from baseline in QTcF and QTcB:

- ≤ 30 msec
- $> 30 - 60$ msec
- > 60 msec

The number of subjects in each group will be summarized for each dosing group.

Subjects will also be categorized into the following groups per their maximum post baseline QTcF and QTcB

- ≤ 450 msec
- $> 450 - 480$ msec
- $> 480 - 500$ msec
- > 500 msec

The number of subjects in each group will be summarized for each dosing group.

Summaries over time and/or changes from baseline over time will also be provided. The relationship between serum concentration of REMD-477 and change from baseline in QTcF and QTcB will be explored graphically; if both QTcF and QTcB exhibit similar relationships, only the QTcF graph will be provided.

The change from baseline of QT interval will be analyzed with a repeated measures analysis of covariance. Dependent variables will be treatment, time and the treatment by time interaction. The change from baseline of the RR interval will serve as a covariate. Subject will be used as a random effect. The estimated treatment mean when change in RR interval equals 0 will be presented for each time. Also, the difference from placebo, the 90% confidence interval of the difference from placebo, and p-value associated with the null-hypothesis of no difference will be presented at each time.

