10.3.4 Efficacy and Pharmacodynamic Statistical Methodology

10.3.4.1 General

All data, including derived parameters, will be listed and summarized for Part A and B separately. Absolute changes (and percentage changes, where applicable) from baseline will also be listed and summarized. Values outside the reference ranges will be flagged, if appropriate.

Preliminary analyses of variance will be performed to assess whether the baseline average daily insulin use and HbA1c levels among subjects are similar between the treatment groups. If any significant difference exists between any two treatments at the 5% level ($p \leq 0.05$), the variable will be used as a covariate in the repeated measures analysis of covariance (ANCOVA) as described in this section to adjust for any pre-intervention difference between treatment groups.

In all analyses, careful attention will be given to the appropriateness of the statistical procedure by determining whether necessary conditions are satisfied; e.g., normality and equal variance. When conditions are violated, the use of data transformations intended to produce data that satisfy normality and equal variance assumptions will be explored. If an appropriate transformation cannot be found, non-parametric methods may be used as an alternative to the more standard analyses.

For all repeated measures ANCOVA of efficacy and pharmacodynamic endpoints, the SAS codes used will be similar to the following:

```
proc mixed data=xxx;
class subject day treatment;
model variable = baseline subject treatment day treatment*day;
repeated day / subject=subject type=csh;
lsmeans treatment*day / pdiff cl alpha=0.05;
ods output lsmeans=lsm;
ods output diffs=diff;
run;
```

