10.3.4.2 Efficacy - Daily Insulin Use

Hypothesis:

Multiple doses of REMD-477 will significantly decrease daily insulin use versus placebo treatment at Week 12.

The daily insulin use will be derived as the average daily insulin over a collection period ranging from either 3 or 7 days. For the Lead-In Period (Part A – 14 to 28 days; Part B – 7 to 14 days), the average daily insulin use will be derived from a period of 14 days. For Days 1, 8, 15, and 22, the average daily insulin use will be derived from the individual insulin values over the next 7 days. For Days 50, 78, 106 and 134, the average daily insulin use will be derived from the individual insulin values over the next 3 days. Baseline assessment is the derived average daily insulin use during the Lead-In (Part A – 14 to 28 days; Part B – 7 to 14 days) period. The measurements will be summarized separately for Parts A and B by treatment group and timepoint along with changes and percentage changes from baseline. Figures of mean average daily insulin use, changes and percentage changes from baseline will be presented separately for Parts A and B by treatment.

The changes from baseline and percentage change from baseline measurements will be statistical analyzed separately for Parts A and B. The statistical analysis for the changes from baseline measurements will be used to test the primary hypothesis, while the statistical analysis for the percentage changes from baseline measurements will be used as a sensitivity analysis. A sequential stepwise hypothesis and a Hochberg testing procedure will be utilized to allow for multiple testing while preserving the overall significance level of the trial.

For Parts A and B separately a repeated measures ANCOVA will be used to compare the changes and percentage changes from baseline in daily insulin use between treatment groups for each timepoint. Dependent variables will be treatment, day, and the treatment by day interaction. The baseline variable will be used as a covariate. Covariates may be added to the above model depending on the results from the comparison of baseline characteristics as detailed in section [10.3.4.1](#)

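### SAP 10.4.4: the QT model is the only repeated measures ANCOVA without its own baseline; adding baseline QT and RR would improve precision modestly on average, once the subject term in the code is corrected

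*SAP*

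**What the plan says.** SAP 10.4.4 sets out the QT analysis as follows: "For Parts A and B separately the change from baseline of QT interval will be analyzed with a repeated measures ANCOVA". The model terms are treatment, timepoint and their interaction, and the only covariate is change in RR: "The change from baseline of the RR interval will serve as a covariate". The example code agrees: "model chg = chg_rr subject trtan day treatment*day". It has no baseline term. The Electrocardiogram part of Protocol section 10 specifies the same single covariate, so the SAP follows the protocol here.

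The QTcF analysis later in SAP 10.4.4 does adjust for baseline: "The baseline QTcF will serve as a covariate". So does daily insulin use in SAP 10.3.4.2: "The baseline variable will be used as a covariate". The same provision appears in SAP 10.3.4.3 to 10.3.4.6 (glucose and MMTT measures, CGM, hormones, HbA1c), 10.4.2 (LDL) and 10.4.3 (vital signs). The general code in SAP 10.3.4.1 has it too: "model variable = baseline subject treatment day treatment*day".

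The documents disagree on the role of subject. For QT, the protocol says "Subject will be used as a random effect". The SAP's QT text says only that day is a repeated measure within subject. The SAP code lists SUBJECT as a CLASS variable and puts it on the MODEL line, which makes it a fixed effect.

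**The concern.** Change in RR accounts for heart rate. It does not stand in for the subject's starting QT. A change score without its baseline in effect fixes the coefficient of baseline at 1. When the within-subject correlation rho is below 1, a fraction (1 - rho) of any chance difference in baseline QT between arms passes into the estimated drug-placebo difference, and the standard error is larger on average than it need be.

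What is at stake is the precision of the QT difference and interval reported at each visit, in Parts of about 25 per arm, and the consistency of one safety model with all the others.

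**Working it through.** **Inputs.** From the documents: 25 per arm in each Part (SAP section 8); five post-baseline ECG visits (Days 29, 57, 71, 85 and 162, Protocol Appendix A). Assumed, because neither document gives them: SD of rate-adjusted QT 10-17 ms between subjects and 7-10 ms between visits.

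**The plan's own figure.** There is none for QT. The 25 per arm comes from the insulin calculation: 2 x (36 x (1.960 + 0.842)/30)^2 = 22.6, so 23 against the stated 22, which is close enough.

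**Step 1: the code as printed.** With 75 subjects and 5 visits there are 375 rows. The columns are 15 treatment-by-day cells, 1 for change in RR and 75 for subjects, 91 in all. Subject columns within an arm add up to that arm's cells, so 3 are redundant and the rank is 88. Residual df are 375 - 88 = 287. Adding baseline QT and baseline RR gives 93 columns, but rank stays 88, residual df stay 287 and the residual sum of squares is identical. Both baselines are constant within subject and so are aliased with the subject terms. The treatment difference at a given day is not estimable with or without them, because treatment is nested in subject.

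**Step 2: the described model, large-sample approximation.** With equal noise at baseline and follow-up:

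- rho = B^2/(B^2 + W^2), where B and W are the between-subject and visit SDs.
- SE of the unadjusted difference in change = sqrt(2/25) x sqrt(2) x W, which is 2.80 ms at W = 7 and 4.00 ms at W = 10.
- Ratio of adjusted to unadjusted SE = sqrt((1 + rho)/2).

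Example at 10/7: rho = 100/149 = 0.671; ratio = sqrt(0.836) = 0.914; reduction 8.6%.

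**Step 3: the cost of estimating two more coefficients.** Simulations with 25 per arm, 4000 runs per cell and adjustment for change in RR throughout (two sets of runs) give the mean reductions in the last column.

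| SD between/visit (ms) | rho | Large-sample reduction | Simulated reduction |
|---|---|---|---|
| 10/10 | 0.50 | 13.4% | 11.1-11.7% |
| 14/10 | 0.66 | 8.8% | 6.8-7.3% |
| 10/7 | 0.67 | 8.6% | 5.4-6.7% |
| 17/10 | 0.74 | 6.6% | 4.4-5.3% |
| 14/7 | 0.80 | 5.1% | 3.0-3.1% |
| 17/7 | 0.86 | 3.7% | 1.4-1.9% |

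The adjusted SE was the larger one in roughly 4% to 40% of single simulated trials, most often at high rho.

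**Step 4: a repeated-measures check with subject random.** This used other assumptions: rate-adjusted QT SD 18 ms, RR SD 120 ms, slope 0.12, 400 runs per setting. The ratio of 95% half-widths with and without the baselines was 0.81, 0.88, 0.93, 0.98 and 1.00 at rho 0.3, 0.5, 0.7, 0.9 and 0.97. The interval was wider in 0%, 0%, 1%, 26% and 60% of runs. Two df move the t quantile only from 1.9935 to 1.9944. Covariates that explain nothing would inflate the variance by about 2.9% (2/69), or about 1.4% on the SE.

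**Step 5: chance imbalance at 10/7.** One standard error of baseline imbalance is sqrt(2/25) x sqrt(149) = 3.5 ms. The share passed on is 0.329 x 3.45 = 1.1 ms in the QT difference.

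**The case against.** The strongest objection is that, in the code as printed, adding the baselines changes nothing. Step 1 confirms this, and the same aliasing affects the baseline terms in the SAP's other coded models. But that code cannot produce the treatment-by-day differences the SAP promises. It is offered as an abbreviated example, and it uses a treatment name and a visit name that are missing from its CLASS statement. It has to be corrected to match the text in any case, and once corrected the omission matters.

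Other parts of the objection stand:

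- A reader might infer that the adjustment is free and always narrows the interval. Steps 3 and 4 show that it does so only on average, at a small cost.
- A reader might infer that these intervals serve to exclude a QT effect. Neither document states a QT margin or hypothesis; they plan a difference, an interval and a p-value against no difference. A baseline-adjusted QTcF analysis and categorical outlier tables are also planned.
- A reader might infer bias. Under randomisation, leaving out baseline does not bias the arm comparison on average.
- The equal-noise assumption may flatter the gain. SAP 10.1.1 averages triplicates for baseline, and the protocol's ECG section makes later ECGs single tracings, although the Appendix A footnotes say triplicate. In the extreme case where averaging cuts baseline noise variance to one third, the 10/10 cell becomes sqrt((200 - 10000/133.3)/133.3) = sqrt(125/133.3) = 0.968, a large-sample reduction of 3.2% rather than 13.4%.

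Separately, the protocol specifies 90% intervals for QT and the SAP 95% ("lsmeans trtan*day / pdiff cl alpha=0.05"), and SAP section 12 does not list the change. That widens the interval by about 20% (1.993/1.666 = 1.196), more than the covariates recover in the Step 3 cells. It needs its own resolution and does not answer this point.

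**Conclusion.** The omission is plain in both the text and the code, and it is unexplained. In the model the text describes, adding baseline QT and baseline RR reduces the SE of the arm difference by about 2-12% on average under the assumed SDs, and by less if baseline is measured more precisely than follow-up or if rho approaches 0.97. It also removes the part of the estimate due to chance baseline imbalance. The cost is two degrees of freedom and a slightly wider interval in some single trials.

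The size rests on variances and a correlation that the documents do not give. The documents support a modest gain in the precision of the reported QT differences. They do not support reading it as a guaranteed gain, a bias in the planned comparison or a failed test of QT safety. This is a desirable refinement, not a serious fault.

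**What to change.** In SAP 10.4.4:

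1. Add mean-centred baseline QT and mean-centred baseline RR to the QT model alongside change in RR, in the text and in the code.
2. Take SUBJECT off the MODEL line. Keep the REPEATED statement, or use RANDOM, so that the code matches the described model and the treatment-by-day differences are estimable.
3. Keep the estimate at zero change in RR, evaluated at the mean baseline values. Centring does this. Uncentred terms without coefficients in the ESTIMATE statement would be evaluated at a baseline QT and RR of zero.
4. Make the treatment and visit names agree across the CLASS, MODEL, LSMEANS and ESTIMATE statements.
5. Record the added covariates in SAP section 12, because the protocol names change in RR only.

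The cost is a few lines of text and code. Baseline QT and RR are already collected, so no new data or visits are needed.

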4 INTRODUCTION

This SAP has been developed after review of the clinical study protocol (Final Version 1.0 dated 03 April 2017 and Protocol Amendment 2 dated 26 October 2019).

This SAP describes the planned analysis of the efficacy, PD, safety, and tolerability data from this study. A detailed description of the planned TFLs to be presented in the Clinical Study Report (CSR) is provided in the accompanying TFL shell document.

The intent of this document is to provide guidance for the statistical analyses of safety, tolerability, efficacy, PK and PD data. In general, the analyses are based on information from the protocol, unless they have been modified by agreement between REMD Biotherapeutics and Covance Early Clinical (EC) Biometrics. A limited amount of information concerning this study (eg, objectives, study design) is given to help the reader's interpretation. This SAP must be finalized prior to the lock of the clinical database for this study. When the SAP and TFL shells are agreed upon and finalized, they will serve as the template for this study's CSR.

This SAP supersedes the statistical considerations identified in the protocol; where considerations are substantially different, they will be so identified. If additional analyses are required to supplement the planned analyses described in this SAP, they may be performed and will be identified in the CSR. Any substantial deviations from this SAP will be agreed upon between REMD Biotherapeutics and Covance EC Biometrics and identified in the CSR.

This SAP is written with consideration of the recommendations outlined in the International Conference on Harmonisation (ICH) E9 guideline entitled, "Guidance for Industry: Statistical Principles for Clinical Trials" and the ICH E3 guideline entitled, "Guidance for Industry: Structure and Content of Clinical Study Reports."^{1,2}

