10.4.3 Vital Signs

The vital signs data (blood pressure, respiratory rate, pulse rate and body temperature) will be summarized separately for Parts A and B by treatment, together with changes from baseline (see Section 10.1.1 for definitions of baseline). Figures of mean vital signs and its changes from baseline will be presented by treatment.

A repeated measures ANCOVA will be used to compare the change from baseline in pulse rate and systolic and diastolic blood pressure results between treatment groups on each day for Parts A and B separately. Dependent variables will be treatment, day, and the treatment by day interaction. The baseline variable will be used as a covariate.

Subject will be used as a random effect. The LS means for each treatment will be presented for each timepoint. Also, the difference from placebo, the 95% confidence interval of the difference

from placebo, and p-value associated with the null-hypothesis of no difference will be for each day.

The SAS code will be similar to as shown below:

```
proc mixed data=xxx;
  class subject day treatment;
  model variable = baseline subject treatment day treatment*day;
  repeated day / subject=subject type=csh;
  lsmeans treatment*day / pdiff cl alpha=0.10;
  ods output lsmeans=lsm;
  ods output diffs=diff;
  run;
```

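### Confidence levels in the SAP's safety models are inconsistent: vital-signs and LDL code gives 90% limits under 95% text, and QT/QTcF moves from the protocol's 90% to 95% without being listed

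*SAP*

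**What the plan says.** **Protocol, Section 10, Safety Analysis.** Two confidence levels are used in neighbouring analyses. For heart rate and blood pressure (Vital Signs): "Also, the difference from placebo, the 95% confidence interval of the difference from placebo". For the change in QT, and again for the change in QTcF (Electrocardiogram): "Also, the difference from placebo, the 90% confidence interval of the difference from placebo".

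**SAP 10.4.3 (vital signs).** The text states a 95% interval for pulse rate and for systolic and diastolic blood pressure. The code beneath it reads "lsmeans treatment*day / pdiff cl alpha=0.10".

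**SAP 10.4.2 (LDL cholesterol).** The same pairing appears: 95% in the text and `alpha=0.10` in the code. The protocol has no LDL model. The SAP adds this analysis and says so in Section 12.

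**SAP 10.4.4 (ECG).** For both QT and QTcF the text says: "Also, the difference from placebo, the 95% CI of the difference from placebo". The QT code has "lsmeans trtan*day / pdiff cl alpha=0.05", and the QTcF code has the same value.

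**SAP Section 4.** The SAP supersedes the protocol's statistical considerations, and "where considerations are substantially different, they will be so identified". Section 12 lists three changes: the model for the glucose-insulin ratio product, the definition of a hypoglycemic event, and the added LDL analysis. It mentions neither a confidence level nor the ECG analysis.

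**The concern.** There are two separate problems.

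1. **Vital signs and LDL.** The SAP disagrees with itself. A programmer who follows the code will print 90% limits, while the table shell and the text call them 95%. The supersession clause cannot settle this, because both statements are in the SAP.
2. **QT and QTcF.** The SAP agrees with itself but departs from the protocol, and the place reserved for such departures does not mention it. A reader of the study report who compares it with the protocol will find a different interval and no reason for it.

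At stake is whether the safety intervals mean what their labels say, and whether the change in the cardiac analysis can be traced. No efficacy conclusion is involved.

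**Working it through.** **Step 1: level implied by each line of code.** In the `lsmeans` statement, the `cl alpha=` option gives limits at level 100 × (1 − alpha)%. So `alpha=0.05` gives 95% and `alpha=0.10` gives 90%.

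| Analysis | Protocol Section 10 | SAP text | SAP code | Level the code gives |
|---|---|---|---|---|
| Heart/pulse rate, blood pressure | 95% | 95% | 0.10 | 90% |
| LDL cholesterol | not in protocol | 95% | 0.10 | 90% |
| QT | 90% | 95% | 0.05 | 95% |
| QTcF | 90% | 95% | 0.05 | 95% |

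As a comparison, the efficacy template in SAP 10.3.4.1 has `alpha=0.05`, which matches the 95% text of the efficacy sections that use it. The text/code conflict is confined to LDL and vital signs. The unlisted departure from the protocol is confined to QT and QTcF.

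**Step 2: effect on interval width.** The normal multipliers are 1.645 for 90% and 1.960 for 95%.

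- Vital signs and LDL, run as coded: 1.645/1.960 = 0.839, so the limits are about 16% narrower than a true 95% interval. With t quantiles at 48, 72 and 200 degrees of freedom the ratio is 0.834, 0.836 and 0.838.
- QT and QTcF, against the protocol: 1.960/1.645 = 1.192, so the intervals are about 19% wider. With t quantiles at the same degrees of freedom the ratio is 1.199, 1.196 and 1.193.

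**Step 3: what this could mean in milliseconds.** Neither document gives a standard deviation for the QTcF change, so I assume a range of 10, 15 or 20 ms. I use the planned 25 per group in each part and a simple two-group comparison, SE = SD × √(2/25).

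| Assumed SD (ms) | SE (ms) | 90% half-width, 1.645 × SE | 95% half-width, 1.960 × SE | Shift of each limit |
|---|---|---|---|---|
| 10 | 2.83 | 4.7 | 5.5 | 0.9 |
| 15 | 4.24 | 7.0 | 8.3 | 1.3 |
| 20 | 5.66 | 9.3 | 11.1 | 1.8 |

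Shifts are computed from unrounded values. The upper limit corresponds to a one-sided 5% error at the protocol's level and 2.5% at the SAP's.

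**Step 4: what does not move.** The alpha option affects only the printed limits. The least-squares means, the differences from placebo and their p-values are the same under either value. The categorical QTc tables do not use it.

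**The case against.** The strongest reply has four parts.

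- **The SAP supersedes the protocol, so 95% for QT and QTcF may be a decision.** This is fair. Text and code agree for both parameters, which fits a deliberate move. The promise to identify differences also covers only substantial ones, and whether a confidence level on a by-visit safety comparison is substantial is a matter of judgement. Even so, Section 12 records an added LDL model and a model change for one secondary metric. A changed level in the cardiac analysis belongs in the same list.
- **The code is only a sample.** SAP 10.4.3 presents it as similar to what will be run. That makes the vital-signs and LDL problem a coding slip in the plan rather than a change of plan, but it is still the code a programmer would start from.
- **The values were simply swapped.** Relative to the protocol, the vital-signs and ECG alphas are exactly exchanged, so a reader might infer a transposition. The documents do not support that. A swap confined to code would have left the ECG text at 90%, and it says 95% for both QT and QTcF. LDL carries the same `alpha=0.10` although it has no protocol level to be swapped with. A copied code block would explain LDL and vital signs equally well.
- **The wider QT interval does no harm.** A reader might infer that 95% makes it harder to exclude a QT increase. Neither document sets a QT margin or a decision based on the limit, and the planned p-value tests no difference. So this is not a planned decision that the change would affect.

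**Conclusion.** The point holds as a correction to reported intervals. It is minor in consequence but definite.

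- **Vital signs and LDL:** the SAP contradicts itself. Following the code gives limits about 16% too narrow for their 95% label.
- **QT and QTcF:** the SAP's intervals are about 19% wider than the protocol specifies, and the change is not listed. Whether it was deliberate cannot be told from the documents.

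The percentages rest only on normal quantiles, and t quantiles change them by less than one percentage point. The shift of about 0.9 to 1.8 ms in each QTcF limit rests on the assumed standard deviations of 10 to 20 ms and a simple two-group standard error. The fix does not depend on how the discrepancies arose.

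**What to change.** 1. In SAP 10.4.2 (LDL) and 10.4.3 (vital signs), change `alpha=0.10` to `alpha=0.05` so that the code matches the 95% text.
2. For QT and QTcF in SAP 10.4.4, choose one of two routes:
   - restore the protocol's 90% in both text statements and set `alpha=0.10` in both code blocks; or
   - keep 95%, add an entry with a reason to Section 12, and report the protocol's 90% interval alongside.
3. Check that the column labels in the table shells match the level finally chosen for each analysis.

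The cost is two code values for item 1. Item 2 costs either two further code values and two text edits, or one Section 12 entry and an extra pair of limits in the QT and QTcF tables. No data collection or sample size is affected. All of it can be done before database lock, by which time the SAP must be final.
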